3.1.1. ITT Analysis Set (Patients 12-70 Years)

Since AQLQ +12 has only been validated for patients aged 12 to 70 years, the analysis of this variable will be restricted to the subset of the ITT analysis set within the specified age range (12 to 70 years) at baseline.

3.2. Safety Analysis Set

The safety analysis set will include all patients who receive at least 1 dose of study drug. In this population, treatment will be based upon the treatment patients actually received, regardless of the treatment to which they were randomized. Patients dosed in error, but who otherwise received at least 1 dose of reslizumab, will be assigned to reslizumab for the analysis of safety.

In this analysis, data collected from patients during the treatment period will be included, up to the point at which patients discontinue from their assigned study treatment. For patients who completed treatment in this study, the treatment period will be defined from the first dose of study drug to the end of treatment (week 24) visit. For patients who prematurely discontinue treatment, the treatment period will be defined from the first dose of study drug to the last dose of study drug + 4 weeks. This analysis will be used as the default approach for all safety endpoints.

3.3. Per-Protocol Analysis Set

The per-protocol (PP) analysis set is a subset of the ITT analysis set including only patients without major protocol violations. The PP analysis set will only be presented for the primary endpoint. In this analysis, data collected from patients during the treatment period will be included, up to the point at which patients discontinue from their assigned study treatment.

3.3.1. Major Protocol Violations

Table 5 presents the planned list of major protocol violations prospectively identified as having the potential to influence and/or bias the primary efficacy results. A complete list of protocol violations resulting in exclusion of patients from the PP analysis will be determined at the end of the study based on team review of accumulated blinded study data. Updates to the following list will be documented in the minutes from the final Statistical Data Review meeting.

Table 5: Major Protocol Violations

Violation	Approach to identifying protocol violations
Patient was not on a daily maintenance dose of OCS prior to screening	Inclusion criteria (c); disposition CRF Medication CRF Protocol violation CRF
Patient does not have a documented blood eosinophil $\geq 300/\mu\text{L}$	Inclusion criteria (d); disposition CRF Laboratory data (for eosinophils obtained during the screening and optimization periods) Subject status CRF (for historical eosinophils) Protocol violation CRF
Patient was not on ICS (at least 880 μg of inhaled fluticasone propionate or equivalent) plus another controller at baseline (eg, LABA, LAMA, LTRA, or theophylline). For patients 12 through <18 years, ICS dose must correspond to at least a medium total daily ICS dose.	Inclusion criteria (e); disposition CRF Medication CRF Protocol violation CRF
Patient does not demonstrate FEV ₁ reversibility ($\geq 12\%$) after administration of inhaled SABA	Inclusion criteria (f); disposition CRF Spirometry data Protocol violation CRF Note: Historical reversibility is acceptable.
Patients who were unblinded at any point during the study	Protocol violation CRF
Patients who received the incorrect study treatment at any point during the study	Protocol violation CRF

3.4. Subgroup Analysis Sets

3.4.1. Age Strata

Selected efficacy endpoints including OCS dose (primary), pre-bronchodilator FEV₁, AQLQ+12, ACQ-6, and blood eosinophils will be analyzed separately for patients aged 12 to <18 years and ≥18 years. Age strata will be defined based on the age recorded in the clinical database.

3.4.2. OCS Strata

Selected efficacy endpoints including OCS dose (primary), pre-bronchodilator FEV₁, AQLQ+12, ACQ-6, and blood eosinophils will be analyzed separately for patients taking an optimized baseline dose of OCS ≤10 mg and >10 mg. OCS strata will be defined based on the optimized baseline dose of OCS recorded in the clinical database.

3.4.3. Other Subgroups

Selected efficacy endpoints including OCS dose (primary), pre-bronchodilator FEV₁, AQLQ+12, ACQ-6, and blood eosinophils will also be examined for the following demographic subgroups:

- Gender (Male, Female)
- Race (White, Black, Asian, Other; Black, non-Black)
- Region (North America, Eastern Europe, Western Europe, Latin America, Asia/Pacific, Middle East/Africa; US, non-US)
- Phadiatop result (Positive, Negative)
- Duration of OCS use (<5, ≥5 years)
- ADA status (Positive, Negative) – for reslizumab-treated patients only

4. GENERAL ISSUES FOR DATA ANALYSIS

4.1. General

Descriptive statistics for continuous variables include number of patients (n), mean, standard deviation (SD), standard error (SE) of the mean, median, minimum, and maximum. If inferential statistics are computed, the least square (LS) mean and standard error of the LS mean will be included. Descriptive statistics for categorical variables include patient counts and percentages.

4.2. Specification of Baseline Values

4.2.1. Oral Corticosteroid Dose

The baseline value is the prescribed optimized OCS dose following the optimization period and will be defined as the OCS dose reported on the day of first dose of study drug.

4.2.2. Diary

Baseline for diary variables (eg, PEF, total asthma symptom score, total reliever use) will be derived as the average of the run-in values over the 7 days preceding baseline/DoR (see [Table 6](#) for the definition of analysis days for diary data). At least 4 out of the 7 expected measurements need to be recorded for each diary variable; otherwise the baseline value for that variable will be treated as missing.

4.2.3. Lung Function

The baseline value for lung function variables (eg, pre-bronchodilator FEV₁, FVC, FEF_{25%-75%}) will be the last observed pre-bronchodilator value prior to the first dose of study drug. Baseline for post-bronchodilator FEV₁ will be the last observed post-bronchodilator value prior to the first dose of study drug.

4.2.4. Patient Reported Outcomes

The baseline value for patient reported variables (eg, ACQ-6, AQLQ +12, SGRQ, EQ-5D) will be the last observed value prior to the first dose of study drug.

4.2.5. Biomarkers

The baseline value for blood eosinophil levels will be the maximum value of the observed assessments from the screening visit to Week -2 (inclusive).

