3.16.2. Procedures Before Study Drug Treatment

3.16.2.1. Procedures During the Optimization Period (Weeks –12 through –3 [Visits 2 through 11])

- Verify that essential screening inclusion criteria for asthma are met before entering optimization
- Perform hematology tests (CBC with differential) if the inclusion criterion of an eosinophil count of 300/ μ L or greater was not met at screening
- Perform brief physical examination
- Perform vital signs assessments
- Provide and collect PEF meter
- Provide/collect electronic asthma control diary; reinforce diary and PEF compliance
- Attempt OCS reduction
- Concomitant medication inquiry
- Adverse event inquiry

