3.16.2.2. Procedures During the Run-In Period (Week –2 [Visit 12])

- Review inclusion/exclusion criteria
- Perform hematology tests (CBC with differential) if the inclusion criterion of an eosinophil count of 300/ μ L or greater was not met at prior visits
- Perform brief physical examination
- Perform vital signs assessments
- Provide/collect electronic asthma control diary; reinforce diary and PEF compliance
- Assess any OCS withdrawal effects (based on investigator's assessment)
- Perform concomitant medication inquiry
- Perform adverse event inquiry

For a minimum of 2 weeks after visit 12, patients will continue on their usual asthma medications and their optimized OCS dose and complete daily self-monitoring of symptoms using an asthma control diary and PEF meter.

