3.16.2.3. Procedures at Baseline/Day of Randomization (Week 0 [Visit 13])

Patients who complete the run-in period will continue to visit 13, when baseline evaluations will be conducted.

The baseline visit (visit 13) will not take place more than 14 weeks after the screening visit. The following procedures will be performed at visit 13 before reslizumab or placebo administration:

- Review inclusion/exclusion criteria
- Review randomization criteria
- Perform urine pregnancy testing (female patients who are not 2 years postmenopausal or surgically sterile only)
- Perform clinical laboratory tests (chemistry and hematology)
- Perform brief physical examination
- Perform vital signs assessments (includes systolic and diastolic blood pressure, pulse, body temperature, and respiratory rate)
- Measure height and weight
- Complete asthma-specific tests
 - Collect and review electronic asthma control diary and reinforce diary and PEF compliance.
 - Pre-bronchodilator spirometry, including FEV₁, % predicted FEV₁, FVC, and FEF_{25%-75%}
 - Post-bronchodilator spirometry, including FEV₁, % predicted FEV₁, FVC, and FEF_{25%-75%}

- Complete the AQLQ+12
- Complete ACQ-6
- Collect blood for asthma biomarker analysis
- Collect blood for serum reslizumab concentration determination (PK assessment)
- Collect blood sample for immunogenicity (ie, ADA) assessment
- [REDACTED]
- [REDACTED]
- Complete EQ-5D
- [REDACTED]
- Complete SGRQ
- Assess CAEs and related health care utilizations
- Collect blood for Phadiatop allergy test ([Vidal et al 2005](#))
- Assess any OCS withdrawal effects (based on investigator’s assessment)
- Record any concomitant medications

A patient who is not randomly assigned to treatment on the basis of the results of baseline/DoR assessments (eg, because entry criteria were not met or enrollment did not occur within the specified time) may be considered for rescreening if there is a change in the patient’s medical background, a modification of study entry criteria, or other relevant change. A patient may be rescreened for this reason 1 time only. The duration between the first visit during the screening period and the rescreening must be >30 days. Patients may be screened again if they did not meet spirometry/reversibility criteria initially.

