9.5.5. Target Biomarker Endpoint

The target biomarker endpoints are the blood eosinophil counts at DoR/baseline; weeks 4, 8, 12, 16, 20, 24 or early withdrawal; and at the follow-up visit (approximately week 32).

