2.2.4. Target Biomarker Endpoint

The target biomarker endpoints are the blood eosinophil counts at DoR/baseline; weeks 4, 8, 12, 16, 20, and 24 or early withdrawal; and at the follow-up visit (approximately week 32).

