8.2. Pharmacodynamic Analysis

8.2.1. Target Biomarker (Blood Eosinophil Counts)

The target biomarker endpoints are the blood eosinophil counts at baseline/DoR; weeks 4, 8, 12, 16, 20, 24 or early withdrawal; and at the follow-up visit (approximately week 32).

Summary statistics of actual values, change from baseline, and percent change from baseline to each scheduled visit will be provided by treatment group, using the ITT analysis set. A line graph will be provided summarizing the mean blood eosinophil counts at each visit.

Blood eosinophils will additionally be examined for selected subgroups defined in Section 3.4. As described above, the analysis of eosinophils by subgroups will be summarized descriptively.

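### SAP 4.2.5 takes the highest pre-randomization eosinophil count as baseline and omits the pre-dose DoR count, so the descriptive change from baseline is biased in a direction the plan does not fix

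*SAP*

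**What the plan says.** SAP 4.2.5 defines the analysis baseline: "The baseline value for blood eosinophil levels will be the maximum value of the observed assessments from the screening visit to Week -2 (inclusive". DoR is visit 13 (week 0), so its count falls outside that window.

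Other sections point to DoR. SAP 2.2.4: "The target biomarker endpoints are the blood eosinophil counts at DoR/baseline". SAP 8.2.1: "The target biomarker endpoints are the blood eosinophil counts at baseline/DoR". Protocol 2.3.4 and 9.5.5 agree; the latter lists "blood eosinophil counts at DoR/baseline; weeks 4, 8, 12, 16, 20, 24 or early withdrawal". Protocol 3.16.2.3 instructs sites at visit 13, before study drug, without condition: "Perform clinical laboratory tests (chemistry and hematology".

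The baseline feeds SAP 8.2.1: "Summary statistics of actual values, change from baseline, and percent change from baseline to each scheduled visit will be provided by treatment group". Eosinophils are also examined descriptively by subgroup. No model or test is attached.

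Two rules govern how many counts enter the maximum. Protocol 3.16.2.1 asks for a CBC in optimization only if a count of 300/µL "or greater was not met at screening", and 3.16.2.2 asks for one at visit 12 (V12) only if it "or greater was not met at prior visits". The schedule (Protocol Table 5, SAP Table 4) marks a CBC at V12 without that condition, and its footnote h relaxes repeats only for the optimization period.

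**The concern.** A baseline should describe the patient's level when treatment starts. The 4.2.5 maximum differs from that level in three ways.

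- **It is a maximum.** With ordinary within-patient variation, the highest of several readings exceeds the underlying level, and more so with more readings. The number of readings varies by patient and by the rule a site follows.
- **It spans a changing OCS dose.** SAP 2.1.2 itself anticipates counts of 300/µL or more emerging as prednisone is reduced. A patient who qualifies at screening may contribute only a pre-taper count, which can lie below the level at DoR.
- **It is partly selected.** Many patients enter because one of these same readings reached 300/µL.

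The DoR count follows at least two weeks of run-in on the optimized dose and is not used for eligibility.

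At stake is the main description of the target biomarker. A placebo arm whose counts do not change after DoR could display a fall or a rise produced only by the baseline rule. Safety tables would also carry a different baseline for the same analyte, because SAP 4.2.6 uses the last pre-dose value and SAP Table 11 lists eosinophils with a change criterion. That is not a direct conflict, but it is confusing.

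**Working it through.** **The plan's own figures.** None is given for eosinophils. The one design figure, 76 per group for 90% power, does not depend on this point. It reproduces with the ordinal-data formula n = 6(z_α/2 + z_β)² / [ln(OR)²(1 − Σp̄³)] = 6 × 10.507 / (0.935 × 0.902) = 74.7 per group; 76 gives 90.5% power.

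**Effect of a maximum alone.** For two lognormal readings at a constant level, E(max)/mean = 2Φ(σ/√2), with σ² = ln(1 + CV²). For an assumed within-patient CV of 30%, σ = 0.294 and the ratio is 1.16; for 50%, σ = 0.472 and the ratio is 1.26. With six readings, simulation gives 1.41 and 1.71.

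**Adding the taper and the 300/µL selection.** Lognormal simulation, 400,000 patients per setting. Assumptions, none from the documents:

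- patient median 300 or 400/µL; between-patient log-SD 0.4 to 0.6; within-patient log-SD 0.2 to 0.5;
- up to 12 readings (V1 to V12), with a log-linear rise of 0, 25, 50 or 100% from V1 to V12;
- DoR and later counts at the V12 level, with no treatment effect, so the true change is 0%.

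Shift s = median of 100 × (post/baseline − 1). The cases are (i) CBC repeated only until 300/µL is met, (ii) CBC at V1 and V12 in everyone, and (iii) eligible on a historical count with a screening CBC only. In (i) and (ii) patients are kept if the maximum reaches 300. Results at median 300 and between-patient log-SD 0.5, for within-patient log-SD 0.2 / 0.3 / 0.4 / 0.5:

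| Rise V1 to V12 | (i) | (ii) | (iii) |
|---|---|---|---|
| 0% | -11.5 / -19.5 / -26.9 / -33.1 | -13.6 / -21.0 / -27.7 / -34.2 | 0 |
| 25% | +7.0 / -2.6 / -10.7 / -18.3 | -6.0 / -12.6 / -19.2 / -25.7 | +25 |
| 50% | +24.3 / +13.8 / +5.0 / -3.2 | -3.3 / -7.7 / -13.5 / -19.5 | +50 |
| 100% | +59.7 / +47.3 / +36.2 / +26.1 | -1.5 / -3.5 / -7.1 / -11.6 | +100 |

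Over the wider set of medians and SDs:

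- (i) -33% to -7%, -18% to +15%, -3% to +36% and +26% to +80% for rises of 0, 25, 50 and 100%;
- (ii) -35% to -12%, -26% to -5%, -19% to -2% and -12% to 0%;
- DoR baseline: within 0.4 points of 0% in every setting of (i) and (ii).

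Under (i), in the tabulated setting, the sign turns at a rise of about 16%, 29%, 42% and 55% for the four within-patient SDs.

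**A second set of assumptions** (geometric mean 250 to 400/µL, between-patient log-SD 0.6 to 0.7, CV 30 to 50%, four optimization draws, 30% eligible on history) gives the same pattern. Stopping once the criterion is met gives -8% to -22% with no rise and +20% to +45% if counts double. V1 plus V12 gives -5% to -30%. All six draws give -21% to -47%.

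**Between-arm consequences.** The baseline precedes randomization, so the absolute difference in change has the same expectation under either baseline. Percent change does not cancel, because the denominator is wrong. With an assumed true fall of 80% on drug and 0% on placebo, the displayed gap in medians is 80 × (1 + s):

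- (i) 80 × (1 − 0.334) = 53 to 80 × (1 + 0.799) = 144 points;
- (ii) 80 × (1 − 0.347) = 52 to 80 × (1 − 0.003) = 80 points.

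**The case against.** The best defence is that DoR/baseline in the endpoint lists is a visit label, that 4.2.5 is the only rule defining the analysis baseline, and that the SAP prevails over the protocol. The precedence rule does dispose of the protocol sections as separate conflicts. It does not settle 4.2.5 against 2.2.4 and 8.2.1, which are all in the SAP. Even read as a pure rule, the maximum still displaces the summaries.

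Second, the 0% under a DoR baseline follows from assuming no change after DoR. OCS is tapered again from week 4 to week 20, and if placebo counts rise 25% over that taper, a DoR baseline shows about +25%. This stands. The DoR count removes the maximum and selection error; it does not separate drug effect from OCS withdrawal.

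Third, the model sets V12 equal to DoR. A V12 count drawn on the day optimization ends may precede the effect of a restored dose. This also stands as a limit. Such a count would tend to raise the maximum further, which is another reason to prefer DoR.

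Fourth, footnote h could be read to cover V12, since the documents describe week -2 as both the end of optimization and the start of run-in. Then case (i) governs, where the sign is least predictable.

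Finally, the analysis is descriptive, no between-arm contrast in percent change is formally planned, and every magnitude is assumed. All true, and the reason the rating is low.

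**Conclusion.** The concern holds, as a minor point. It is certain from the text that the rule takes a maximum, leaves out an unconditional pre-dose DoR count, and does not match the time point SAP 2.2.4 and 8.2.1 name. That this shifts within-arm change and percent change follows from the rule.

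The size and sign cannot be derived from the documents. Under the stated assumptions the shift is downward when counts are stable, and in the settings tried also when a V12 count exists for everyone. It can be upward when counts rise over the taper and later CBCs are drawn only while 300/µL is unmet. Percent-change comparisons between arms are distorted in the same way. Actual post-baseline values, the planned line graph of mean counts, absolute between-arm differences (in expectation), the sample size, and primary and secondary inference are untouched.

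**What to change.** In SAP 4.2.5, define the eosinophil baseline as the pre-dose DoR count, or the last value before first dose if the DoR count is missing. Report the screening-to-week -2 maximum separately, labelled as an eligibility or descriptive characteristic. This aligns 4.2.5 with 2.2.4 and 8.2.1, follows the last-pre-dose convention of 4.2.3 and 4.2.4, and gives eosinophils the same baseline in the biomarker and safety tables.

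The cost is one line of SAP text plus cross-references. The sample is already collected, and nothing changes in power or error control. Because the retained maximum would still depend on how often a CBC was drawn, the V2 to V12 instructions in the schedule table and in Protocol 3.16.2.1 and 3.16.2.2 should be reconciled, or the number of contributing counts reported beside it.

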4.2.6. Safety

The baseline value for all visit-based safety assessments (eg, laboratory, vital signs) will be the last observed value prior to the first dose of study drug.

4.3. Multiple Comparisons and Multiplicity

A fixed sequence multiple testing procedure will be implemented to test the primary and secondary variables while controlling the overall type I error rate at 0.05. If the resulting

two-sided p-value from the primary comparison is ≤ 0.05 , then the next comparison of interest (first secondary variable) will be interpreted inferentially at 0.05. This process continues through the secondary variables until either all comparisons of interest are interpreted inferentially, or until the point at which the resulting two-sided p-value for a comparison of interest is > 0.05 . At the point where $p > 0.05$, no further comparisons will be interpreted inferentially. The hierarchy of endpoints is as defined in Section 6.3.1.

No multiplicity adjustments will be made for other efficacy and exploratory analyses.

4.4. Handling Withdrawals and Missing Data

Analysis of the primary and secondary variables related to categorical OCS dose reduction will incorporate missing data as nonresponders, as described in Section 6.2.2 and Section 6.3.2. The primary variable will also be assessed including multiple imputations for missing data as a sensitivity analysis, as described in Section 6.2.3 and Appendix A. For all other variables, only the observed data from the patients will be used in the statistical analyses (ie, there is no plan to estimate missing data).

4.5. Study Days and Visit Windows

Study days will be numbered relative to the first day of study drug administration. The start of treatment (day 1) is defined as the date on which a patient takes the first dose of study drug, as recorded on the study drug diary. Days will be numbered relative to study start (ie, ..., -2, -1, 1, 2, ...) with day 1 being the start of study drug and day -1 being the day before the start of study drug).

For safety-by-visit summaries, if there are multiple assessments at a post-baseline visit then the last non-missing assessment at that visit will be used for the analysis. This includes assessments at the scheduled and unscheduled visits.

‘Endpoint’ for safety analyses and summaries is the time point when the last observation was obtained during the treatment period. For patients who completed treatment in this study, the treatment period will be defined from the first dose of study drug to the end of treatment (week 24) visit. For patients who prematurely discontinue treatment, the treatment period will be defined from the first dose of study drug to the last dose of study drug + 4 weeks.

For efficacy-by-visit summaries, only the assessments at the scheduled visit will be summarized. The assessments at unscheduled visits will be listed. For the purpose of the efficacy analysis, assessments collected at an early termination visit will be considered as the next scheduled visit for that assessment if at least 3 but no more than 5 weeks elapsed since the date of the last medication intake.

Efficacy-by visit summaries will be presented on-treatment. In this context, ‘endpoint’ will be defined as the last observation obtained at a scheduled or qualified early termination visit during the treatment period. For patients who completed treatment in this study, the treatment period will be defined from the first dose of study drug to the end of treatment (week 24) visit. For patients who prematurely discontinue treatment, the treatment period will be defined from the first dose of study drug to the last dose of study drug + 4 weeks.

For selected variables, additional sensitivity analyses may be presented utilizing all data collected over the entire course of the study including data collected after withdrawal for patients who prematurely discontinue from treatment. In this context, ‘endpoint’ will be defined as the last observation obtained at any post-baseline scheduled or qualified early termination visit.

For summaries of diary data (eg, rescue medication use, asthma symptom score), the day used for analysis will consist of the evening assessment for the day and the morning assessment for the following day, as illustrated in Table 6. Weekly average data will be generated using 7-day window intervals derived based on these analysis days.

Table 6: Definition of Analysis Days for Diary Data

Study Period	Diary Day	Study Day ^a	Time Point
Baseline	Day -7	-7	PM
		-6	AM
	Day -6	-6	PM
		-5	AM
	Day -5	-5	PM
		-4	AM
	Day -4	-4	PM
		-3	AM
	Day -3	-3	PM
		-2	AM
	Day -2	-2	PM
		-1	AM
	Day -1	-1	PM
		1 (pre-dose)	AM
Treatment	Day 1	1	PM
		2	AM
	Day 2	2	PM
		3	AM
	PM
		..	AM
	Day 167	167	PM
		168	AM

^a Study Day 1 denotes the first dose of study drug; Study Day -1 is the day prior to the first dose of study drug.

